We assume type I error rates of 2.5% for tests of contrasts between repeated measures within individuals. We anticipate N=40 participants will suffice to detect moderate effects of d=0.5 with 80% power. Effects of this size translate to 0.71 dB points for QuickSIN and 2.6 for ANL. These are smaller than critical differences identified for QuickSIN (2.7 dB) [22] and ANL (6 dB) [23]. A smaller sample size would provide 80% power to detect larger effects (see Table A), though even if we fall short of our recruitment and data collection goals, we will still be well-powered to detect meaningful effects in Aim-1.

Table A. Sample sizes & effect sizes for Aim-1				
Sample Size	Difference (d)	QuickSIN Diff.	ANL Diff.	
30	0.59	0.82	4.12	
35	0.54	0.76	3.79	
40	0.50	0.71	3.53	

Experiment 2 (Aim 2)

We will report 95% confidence intervals for the ICC and Pearson correlations, which will have similar widths (see Table B). A sample size of N=40 would allow for narrow confidence intervals for large ICCs and correlations; and ICC \geq 0.87 or correlation >0.87 would have a 95% confidence interval width <0.15. Smaller ICCs would have larger confidence interval widths; an ICC or correlation of 0.7 would have a 95% confidence interval width of 0.33.

Table B. Pearson correlations, ICC, and corresponding confidence interval (CI) widths for Aim-2			
Correlation	Cor. Cl	ICC	
0.5	0.48	0.5	0.47
0.7	0.33	0.7	0.33
0.8	0.24	0.8	0.23
0.9	0.13	0.9	0.13

4.0 Recruitment and Screening Methods:

Recruitment process:

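### The detectable ANL difference at N=40, d=0.5 and 80% power is 2.6 in the text but 3.53 in Table A, and no SD is given to settle which was meant

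*Combined protocol and SAP*

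**What the plan says.** All the relevant statements are in Section 3.0 (Sample Size), under Experiment 1 (Aim 1).

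- Error rate: "We assume type I error rates of 2.5% for tests of contrasts between repeated measures within individuals". Sidedness is not given.
- Power: "We anticipate N=40 participants will suffice to detect moderate effects of d=0.5 with 80% power".
- Conversion to raw units: "Effects of this size translate to 0.71 dB points for QuickSIN and 2.6 for ANL".
- Benchmark: both detectable differences are said to be below the published critical differences, 2.7 dB for QuickSIN and 6 dB for ANL.
- Table A, whose columns are sample size, d, QuickSIN difference and ANL difference, has the rows "30 0.59 0.82 4.12", "35 0.54 0.76 3.79" and "40 0.50 0.71 3.53".

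The text points to Table A as part of the same power analysis. The supplied documents give no SD for either measure, no within-person correlation, and no source for the conversion from d to raw units.

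**The concern.** At N=40 and d=0.50 the plan gives one QuickSIN figure (0.71 in both places) and two ANL figures (2.6 and 3.53). A raw difference is d times an SD, so with d fixed the two ANL figures need two different SDs. At most one can belong to this calculation.

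QuickSIN and ANL are the two outcomes on which Experiment 1 is powered, so this is the stated sensitivity for one of them, and the text carries the more favourable value. If Table A is right, a reader interpreting a null ANL contrast from the text would believe that a 2.6 difference had been looked for with 80% power when it had not.

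**Working it through.** **Inputs, all from Section 3.0.** Type I error 2.5% per contrast; 80% power; N = 30, 35 and 40; Table A's d, QuickSIN and ANL columns; the text's 0.71 and 2.6; the critical differences of 2.7 dB and 6 dB. Two assumptions are mine: a paired t test, from the within-subjects design, and a two-sided 2.5% level.

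**Step 1: reproduce Table A's d column.** For a paired t test, power is taken from the noncentral t distribution with N−1 degrees of freedom and noncentrality d·√N. Solving for d at 80% power:

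| N | Two-sided 2.5% | One-sided 2.5% | Table A |
|---|---|---|---|
| 30 | 0.5887 | 0.53 | 0.59 |
| 35 | 0.5413 | 0.49 | 0.54 |
| 40 | 0.5038 | 0.45 | 0.50 |

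The two-sided version matches every row and the one-sided version matches none. Power at N=40 and exactly d=0.5 is 79.3%, so the plan's main power statement holds.

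**Step 2: back out the SDs.** SD = raw difference / d, using the unrounded d from Step 1.

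| Source | QuickSIN SD | ANL SD | ANL/QuickSIN |
|---|---|---|---|
| Table A, N=30 | 0.82/0.5887 = 1.39 | 4.12/0.5887 = 7.00 | 4.12/0.82 = 5.02 |
| Table A, N=35 | 0.76/0.5413 = 1.40 | 3.79/0.5413 = 7.00 | 3.79/0.76 = 4.99 |
| Table A, N=40 | 0.71/0.5038 = 1.41 | 3.53/0.5038 = 7.01 | 3.53/0.71 = 4.97 |
| Text, N=40 | 0.71/0.5038 = 1.41 | 2.6/0.5038 = 5.16 | 2.6/0.71 = 3.66 |

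With the rounded d of 0.50, the N=40 ANL SDs are 3.53/0.50 = 7.06 and 2.6/0.50 = 5.20. The conclusion is the same.

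**Step 3: can rounding explain it?** Values that round to 2.6 run from 2.55 to 2.65. The widest SD range they allow is 2.55/0.5038 = 5.06 to 2.65/0.50 = 5.30, well short of 7.0. In the other direction, scaling the N=30 row to any d that rounds to 0.50 gives an ANL difference between 4.12 × 0.495/0.595 = 3.43 and 4.12 × 0.505/0.585 = 3.56. That range does not reach 2.6.

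**Step 4: what follows under each SD.**

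- SD about 7.0: a true ANL difference of 2.6 is d = 2.6/7.0 = 0.37. Power at N=40 is 51.3%, or 50.5% with SD 7.06. With SD 7.06, 80% power would need 73 participants.
- SD about 5.2: power for 2.6 at N=40 is 79.3%, as the text claims, but Table A's ANL column is then wrong. It would read 5.2 × 0.5887 = 3.06, 5.2 × 0.5413 = 2.81 and 5.2 × 0.5038 = 2.62, in place of 4.12, 3.79 and 3.53.
- The 6 dB benchmark under the less favourable SD of 7.0: power is 99.9% at N=40 and 98.8% at N=30.

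**The case against.** The strongest reply is that nothing in the design moves. The sample size is set on standardized d=0.5, which reproduces. The raw-unit figures serve only to show that the detectable effect is below the critical difference, and 2.6, 3.53 and even Table A's largest ANL entry (4.12 at N=30) all meet that test. The plan never names 2.6 as a target, so 51% power at 2.6 answers a question it did not ask, using an SD it did not state. **This stands as a limit on the consequence.** It does not remove the error, because a power statement should not give two incompatible values for one detectable effect.

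A second reply is that the plan does not say what d is standardized by, so treating the SDs as those of paired differences is an interpretation. That is true of the wording. The paired t reading does reproduce all three d values, though, and the 2.6 versus 3.53 conflict exists whichever SD defines d.

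A third is that Table A's rows come from one calculation with one SD, so their agreement is not three independent confirmations of 7.0. **This also stands.** The text's ANL value is the one that departs from the rest, but that does not prove which SD was intended.

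**Conclusion.** The concern holds. For the same N, d and power, the plan gives detectable ANL differences of 2.6 and 3.53, a ratio of 1.36, and neither rounding nor any other statement in the supplied documents reconciles them. The implied SDs are about 5.2 and 7.0. The table is internally consistent and the text's ANL figure is the odd one out, but without a stated SD or source the documents cannot decide between them.

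The conflict itself needs no assumption. The 51% power figure does: it depends on the back-derived SD of about 7.0, a paired t test and a two-sided 2.5% level, the last two inferred because together they reproduce Table A. N=40, the d=0.5 power statement and the comparison with 6 dB are unaffected.

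**What to change.** Confirm which SD was used to convert d into ANL units and where it came from. State it in Section 3.0 together with the QuickSIN SD (about 1.4 by back-calculation), what d is standardized by, and whether the 2.5% level is two-sided. Then make text and table agree:

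- If the ANL SD is about 7.0, change the ANL figure in the text from 2.6 to 3.53 dB and leave Table A as it is.
- If it is about 5.2, keep 2.6 in the text and recompute Table A's ANL column to about 3.06, 2.81 and 2.62.

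The cost is one number or three table cells, plus a sentence giving the SDs and their source. The stated ANL sensitivity may become less favourable. Recruitment, procedures and analysis do not change.

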Experiment 2: To validate the capability of the OSP to assess listener outcomes, we will also compare aided speech discrimination ability in quiet and in noise for two test modes: OSP assessment tool (stimulus presentation controlled by participant & responses collected directly from the participant on the OSP) versus conventional (stimulus presentation controlled on an external program by experimenter & paper-and-pencil responses provided by participant). Statistical analyses methods will quantify agreement, correlation, and association (linear regression) between outcomes from the two test modes.

In both experiments, each participant will be presented with all the test conditions (hearing aid settings or test modes) in a laboratory setting. The order of presentation of the test conditions will be randomized and counterbalanced across participants.

2.0 Enrollment Criteria (who can be in your study and who would not be eligible to participate in your study):

Inclusion Criteria:

- >= 18 years of age; any sex

- Sensorineural hearing loss with pure-tone thresholds between 25-85 dB HL at octave frequencies between 250 and 3000 Hz

- Speak English as their primary language

- Normal or corrected-to-normal vision (<=20/50)
- Participants will be in good health (self-report)

Exclusion Criteria:

- Clinically significant unstable or progressive medical conditions

- Participants who score < 23 on the cognitive screening test (Montreal Cognitive Assessment)

- Evidence of conductive hearing loss or middle ear issues
- Significant history of otologic or neurologic disorders

- Non English-speaking or non-native English speaking

For the purposes of test validation and calibration, we may also enroll a small group (n=50) of listeners with normal hearing, defined as pure-tone thresholds of 25 dB HL or less at octave frequencies between 250 and 3000 Hz. With the exception of having normal hearing, those participants will follow the inclusion and exclusion criteria described above.

The study will not recruit special populations such as adults unable to consent/cognitively impaired, minors, prisoners, or other detained individuals.

3.0 Sample Size:

The proposed study will recruit 100 participants (based on power analysis) with bilateral symmetric sensorineural HL in the mild to severe range, over a 2-year period. Each experiment will recruit approximately 40 participants (additional 10 account for pilot testing and attrition).

Experiment 1 (Aim 1)

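### Experiment 2: at N=40 an ICC or correlation of 0.87 has a 95% confidence interval about 0.16 wide, not below 0.15 as the plan states

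*Combined protocol and SAP*

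**What the plan says.** Experiment 2 compares two test modes, the OSP assessment tool and the conventional method, in the same participants. Its part of section 3.0 states no power calculation. The sample size is supported by the expected width of 95% confidence intervals for the ICC and the Pearson correlation.

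- The general statement: "A sample size of N=40 would allow for narrow confidence intervals for large ICCs and correlations".
- The specific one, applied also to an ICC of 0.87 or more: "correlation >0.87 would have a 95% confidence interval width <0.15".
- A second specific figure: "an ICC or correlation of 0.7 would have a 95% confidence interval width of 0.33".
- Table B, which lists widths at 0.5, 0.7, 0.8 and 0.9 for both statistics. It has no row for 0.87.

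The section does not name the interval formula or the form of ICC.

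**The concern.** The 0.87 figure does not fit the table beside it. Table B puts the correlation width at 0.24 for 0.8 and 0.13 for 0.9. A value of 0.87 lies seven tenths of the way between them, where a width of about 0.16 would be expected.

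Experiment 2 is meant to validate a new assessment tool against a conventional one, so high agreement is the range that matters. This is also the one sentence that ties a particular high coefficient to a bound on the width. A reader who relies on it would expect a tighter interval than 40 participants give.

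**Working it through.** **Inputs**

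- N = 40 and 95% confidence, from section 3.0, Experiment 2. Two-sided intervals are assumed.
- k = 2 measurements per participant for the ICC, from the description of Experiment 2 in the opening section: "we will also compare aided speech discrimination ability in quiet and in noise for two test modes".
- Coefficient 0.87 and width below 0.15, from section 3.0.

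**Formulas**

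- Correlation (Fisher z): limits tanh(atanh(r) ± 1.96/√(N − 3)). At N = 40 the half-width on the z scale is 1.96/√37 = 0.322.
- ICC (one-way, k = 2, F-based): F0 = (1 + ICC)/(1 − ICC). Then FL = F0/1.881 and FU = F0 × 1.885, where 1.881 and 1.885 are the 97.5% points of F(39, 40) and F(40, 39). Each limit is (F − 1)/(F + 1).

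**Step 1: reproduce Table B at N = 40**

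| Coefficient | Correlation, Table B | Fisher z | ICC, Table B | One-way F |
|---|---|---|---|---|
| 0.5 | 0.48 | 0.479 | 0.47 | 0.470 |
| 0.7 | 0.33 | 0.334 | 0.33 | 0.327 |
| 0.8 | 0.24 | 0.239 | 0.23 | 0.234 |
| 0.9 | 0.13 | 0.128 | 0.13 | 0.126 |

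All eight entries agree to two decimals, so these formulas and N = 40 account for the plan's own table.

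**Step 2: the same formulas at 0.87**

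- Correlation: atanh(0.87) = 1.333. The z limits are 1.333 ± 0.322, that is 1.011 and 1.655. Back-transformed they are 0.766 and 0.930, with a width of 0.163 (0.1635 before rounding).
- ICC: F0 = 1.87/0.13 = 14.385, FL = 7.649, FU = 27.12. The limits are 6.649/8.649 = 0.769 and 26.12/28.12 = 0.929, with a width of 0.160.

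**Step 3: where the width drops below 0.15**

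| Coefficient | Correlation width | ICC width |
|---|---|---|
| 0.87 | 0.163 | 0.160 |
| 0.88 | 0.152 | 0.149 |
| 0.89 | 0.140 | 0.137 |

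The crossing points are about 0.882 for the correlation and 0.879 for the ICC. To keep both 0.87 and a width below 0.15, N would have to be 47 for the correlation (0.149) or 45 for the one-way ICC (just under 0.150).

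**Step 4: a check that needs no formula**

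The last two rows of Table B read "0.8 0.24 0.8 0.23" and "0.9 0.13 0.9 0.13". Linear interpolation at 0.87 gives:

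- correlation: 0.24 − 0.7 × (0.24 − 0.13) = 0.163
- ICC: 0.23 − 0.7 × (0.23 − 0.13) = 0.160

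If every entry is taken at the bottom of its rounding range, the results are 0.235 − 0.7 × 0.110 = 0.158 and 0.225 − 0.7 × 0.100 = 0.155. Both are still above 0.15.

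**The case against.** The arithmetic could be rescued only by a different formula, a different N or a different number of ratings. None of these works.

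- **Another formula.** The two-way consistency ICC gives 0.161 at 0.87. It also gives 0.236 at 0.8, which rounds to 0.24 and not to the printed 0.23. Large-sample (Wald-type) widths are the closest, at 0.151 to 0.157, but they still exceed 0.15 and give 0.12 at 0.9 where Table B prints 0.13.
- **A larger N.** At N = 50 the widths at 0.87 would be 0.144 and 0.142. The sentence states N = 40, however, and section 3.0 assigns the additional 10 to pilot testing and attrition. Table B does not fit N = 50 either: the correlation width at 0.5 would be 0.43, against the printed 0.48.
- **More ratings.** Three ratings per participant would give an ICC width of 0.131 at 0.87. The plan compares two modes, and three ratings would give 0.356 at 0.5, against the printed 0.47. The correlation would be unaffected.
- **Rounding.** A coefficient of 0.8749, which rounds to 0.87, still gives a correlation width of 0.158.

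The stronger objection concerns weight, and much of it stands. The excess is about 0.01, and the threshold moves from 0.87 to about 0.88. No decision rule or agreement criterion in the plan uses 0.87 or 0.15. The general statement that N = 40 gives narrow intervals for large coefficients remains fair, and Table B and the 0.7 figure are right. A reader who uses Table B would not be misled. This argues for a modest correction, but it does not make the sentence true.

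**Conclusion.** The sentence is wrong as written. At N = 40 and a coefficient of 0.87 the 95% interval is about 0.163 wide for the correlation and 0.160 for the ICC. Relative to the stated bound this is 0.1635/0.15 = 1.09 and 0.160/0.15 = 1.07, so 7% to 9% too wide. The claim fails from 0.87 up to about 0.882 (correlation) or 0.879 (ICC) and holds above those values.

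The fault is confined to one sentence. It should still be corrected, because interval width is the only justification given for this experiment's sample size and the error overstates the precision.

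The conclusion assumes two-sided 95% intervals and two ratings per participant. The formulas are inferred, since the plan names none, but they account for every entry in Table B.

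**What to change.** Change one figure in section 3.0, Experiment 2, in either of two ways:

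- keep the width below 0.15 and raise the coefficient to at least 0.89, which is safe for both statistics (0.140 and 0.137); or
- keep 0.87 and state the width as about 0.16.

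A change to 0.88 would not be enough, because the correlation width there is 0.152. It would also help to name the interval methods and the form of ICC, so that Table B can be checked directly.

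The cost is an edit to the text and a slightly less favourable precision statement. N = 40, Table B and the planned analyses do not change.

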9.0 Research with Vulnerable Populations: NA

10.0 Incomplete Disclosure or Deception: NA

11.0 Consent Process:

Prior to enrollment in the study, potential participants will have a hearing, vision, and cognitive test with authorization by a screening consent form. These tests will allow us to exclude potential participants who are ineligible based on their hearing, vision, or cognitive status from enrolling in the study. These tests will be built into the first visit tasks and will last 60-80 minutes. If the participant is eligible based on the screening process, he/she will be consented for the experimental procedures using a separate form. If a participant is not eligible based on screening, they will have the option to authorize future contact and authorize the lab to retain the screening audiogram and cognitive test results. Consenting will take place in the Hearing Aid Lab, prior to any research procedure taking place. All consent forms are stored in a locked file cabinet within the Hearing Aid lab (locked lab). The potential participant will be provided unlimited amount of time to review the consent forms and ask any clarifying questions. Following the participant's opportunity to review the consent form, the researcher will review each section with the participant to clarify any study procedure and ensure understanding. All participants will be offered a copy of their signed consent form with the option to decline. The researcher will document the consent process and the participants' receipt of/decline of a signed copy on a study flow sheet. Both participant and staff will initial the flow sheet to verify that the consent form was provided or that a copy was declined. Please note that during the consent process, the researcher will explain to the participant that their identifiable information will be kept confidential and will not be used.

Virtual consent may be obtained as an alternative (e.g., remote participation). Participants will be consented using one of two procedures, determined by participant preference:

Option 1: The participant will be consented electronically using REDCap. The participant will be required to "sign" by typing their name and enter the date. The participant will be able to review the consent form as many times as they need to, go back and forth through sections, and take their time before providing their consent. They may save their progress on the form and return to it at a later time if needed. The participant may contact a study team member as needed to provide any clarifications regarding any part of the consent form via phone or email or video before the deciding to provide their consent. All information required for informed consent will be available on the eConsent forms. Consent forms for this study do not have any associated external material

or hyperlinks. In order to ensure the identity of the signer, the REDCap consent form can only be accessed by the email address that it is sent to (i.e., the email address provided by the participant). In addition, the participant will be provided with a predetermined passcode via phone or video. At the time of accessing the electronic consent form, the participant must enter the passcode which will be internally compared with the stored version entered by the study team member. The participant will be granted entry only if the passcode matches. The participant will have the option of saving a copy of their signed eConsent forms as PDFs. A study team member will review the submitted eConsent form and electronically sign and date as confirmation.

Option 2: The participant will be sent a consent form via encrypted email, which they will sign and date, scan/take a photo of, and email back to the research staff. The participant may contact a study member as needed to provide any clarifications regarding any part of the consent form via phone or email or video before the deciding to provide their consent. The staff member will review the submitted consent form and sign and date as confirmation. The participant will be sent a scanned copy of the signed consent form for their records.

12.0 Waiver of Participant Signature on Consent Form: NA

13.0 Waivers and Alterations of Consent Information: NA

14.0 Financial Compensation:

Upon completion of the study tasks, the participant will be paid an hourly rate for participation (\$15/hour). Payment will be made in cash at the conclusion of each session. If the participant decides to withdraw from the study before its completion, he/she will be paid \$15/hour for the time spent. There is also dedicated parking space for research participants (at no charge) and an accessible entrance to the lab building.

Participants may be given the option of being compensated at the above rate in the form of a Hyperwallet Virtual Card provided by Northwestern University. The card will be issued at the completion of the study visit at which point the participant will be emailed instructions for the card activation process. For participants who do not have access to email, they will also be given the option of being issued a check or a physical gift card for the amount that they are owed. Financial compensation will not be withheld in the event of loss or damage to any experimental equipment.

15.0 Audio/Video Recording/Photography

Audio and video recordings may be obtained during the screening tests and the listening tasks. The purpose of the audio/video recordings is to ensure accuracy

(a second scorer may listen to the recordings and correct any potential errors). The recordings will contain only non-identifiable information and will be destroyed 3 years after the completion of the study. Audio and video recordings will not be obtained during earmold impressions and hearing aid fitting.

16.0 Potential Benefits of this Research:

Participants in this study may not directly benefit from the experiment. The importance of this research lies in the potential to generate innovative and evidence-based solutions to increase access to hearing healthcare. Therefore, participants with hearing loss seeking hearing aids may benefit in the long-term. Many participants are interested in hearing aid research as an opportunity to get information and ask questions about hearing aids without sales pressure. All participants will have the opportunity to receive counseling at the end of the study, by the investigators or the research coordinator, all of whom are also trained and certified audiologists. Counseling, if and when provided, will include listening recommendations tailored to their individual speech understanding and memory. Participants will have the chance to ask questions and receive information about options for their hearing loss (outside the study).

17.0 Potential Risks to Participants:

All study procedures pose minimal risk to participants. There is potential that the study task might be boring or repetitive, and therefore if a participant wishes to discontinue testing at any point, they may choose to do so without any consequence. Listeners who receive poor scores on the MoCA may be disappointed to learn of their performance. Some listeners may find the sounds processed through the OSP to be sharp or tinny in comparison to their unaided hearing. These are normal and expected consequences of any hearing aid fitting. Loudness discomfort levels will be measured and presentation levels will be monitored to ensure that levels never become uncomfortable.

When the earmold impression is taken, participants may experience some temporary discomfort or a ticklish feeling as the cotton/foam block is placed into the ear canal. Participants may also notice that the impression material is slightly cold, or experience a feeling of pressure while the impression material is in your ear. Rarely, there can be some minor abrasions to the skin of the ear canal. These procedures are routinely used when fitting hearing aids or creating custom earplugs and the risks in this study are no higher than the risks that would be experienced in an audiology clinic.

The hearing aids and earmolds will only be used for the duration of the experiment. The participant is free to remove the hearing aids and/or leave the test booth at any time. Participants are encouraged to take breaks and can discontinue the study at any time without penalty. If the investigator determines

participation in the study places a participant at unacceptable risk, enrollment or study tasks will not proceed.

Participant confidentiality will be ensured by storing data without subject identifiers. Data files are password protected and can only be accessed by authorized lab members. Hard copy data are stored in locked file cabinets within a restricted-access laboratory space. All study staff complete training in ethical procedures for working with human subjects and in HIPAA regulations.

If a research participant decides to withdraw or discontinue study procedures, all data collected up to that point can be used by the investigator unless the participant indicates that they would like to have their data removed from the study. In the event that a participant is removed from the study without their consent, compensation will be pro-rated based on the duration the participant remained compliant with study tasks and procedures.

In the event that a participant is compensated using the Hyperwallet Virtual Card, an account will need to be created using the participant's name and email address, which will link their name to the study. This creates a small additional risk of breach of confidentiality.

18.0 Provisions to Protect Participant Privacy and Data Confidentiality:

All experimental procedures will be conducted in the Hearing Aid Lab at Northwestern University. The data for this study will include audiometric thresholds, age, cognitive measures, speech perception scores, hearing aid fitting data, and acoustic measurements. Participant responses recorded through the computer interface will be coded and will not contain any identifiable information. All data will be de-identified prior to analysis. De-identification will take place by assigning a particular code to all data pertaining to one subject. The link between the subject code and the subject name will be stored in a password-protected file on a HIPAA-approved server managed by Northwestern School of Communication computer support staff. This information will also be stored on the secure REDCap database. Participant identifiers will be stored electronically on REDCap in a separate instrument than the study data. REDCap will also be used to track study data. All research staff will receive appropriate Human Subjects protection training and training regarding confidentiality. Data are only accessible by the study staff via password-protected files. Discussion regarding subject confidentiality will also be included during regular lab meetings.

19.0 Data Monitoring Plan to Ensure the Safety of Participants:

All experimental procedures will be conducted in the Hearing Aid Lab or the virtual sound room at Northwestern University. The data for this study will

include audiological data, age, cognitive measures, and speech perception scores, hearing aid fitting data, and acoustic measurements. Participant responses recorded by the experimenter through the computer interface will be coded and will not contain any identifiable information. Any audio-recording done for the purpose of scoring will also be de-identified and will be deleted at the end of the experiment. All data will be de-identified prior to analysis. Deidentification will take place by assigning a particular code to all data pertaining to one subject. The same subject code will be used in the hearing aid programming software. The link between the subject code and the subject name will be stored in a password-protected file on a HIPAA-approved server managed by Northwestern School of Communication computer support staff. All research staff will receive appropriate Human Subjects protection training and training regarding confidentiality. Data are only accessible by the study staff via password-protected files. Discussion regarding subject confidentiality will also be included during regular lab meetings.

The proposed research uses a very low-risk intervention (i.e., hearing aids). The investigator will be responsible for ensuring participants' safety at the time of experimentation. If the investigator determines that participation in the study places a participant at an unacceptable risk, enrollment or study tasks will not proceed. The participants will use the OSP only for the duration of the experiment. Therefore, the use of the OSP will always be monitored by the experimenter. A trained audiologist is responsible for making the ear impressions and completing the OSP fitting. All testing will be conducted by an investigator, an audiologist, the research study coordinator, or a research assistant. The research assistant will be supervised by an investigator or the research study coordinator. The investigator as well as the research study coordinator are trained and licensed audiologists and have several years of experience in conducting hearing assessments, hearing aid fitting, and research with adults and are therefore qualified for monitoring the study.

